Beginning on Page 5, the simulation demonstrates for Natesto applied once per day to right and left eyelids, both upper and lower eyelids (11 mg total) that the mean increase in serum levels above baseline of total testosterone is about 0.15 to 0.18 ng/ml, whether for a single application or repeated applications over a 30-day period (Figure 3. A – D). Clark et al.³⁹ have published the weighted average range values for total testosterone (TT, the parameter that is measured during routine clinical laboratory assay) as 2.54 - 8.90 ng/ml for males and 0.12 - 0.58 ng/ml for females. From the simulation, this indicates that male serum TT increase will be minimal and potentially double the minimum normal level for females, yet still possibly within the normal range for females. It is unlikely that any virilization effects (e.g., facial hair growth, scalp hair loss etc.) will be observed in males and it is unknown whether these same effects will occur in females.

[name] has monitored patients who were using testosterone cream applied to the eyelids twice a day for at least 3 years and found no elevation in IOP.⁴¹ In another study, Connor observed that short term treatment with 5% transdermal testosterone cream for

dry eye enhances female patient TBUT but doesn't significantly impact the patient's blood pressure.⁴³

In our proposed study, we will monitor total serum testosterone levels in all subjects at baseline, and within two hours of the morning eyelid dose at the four-week visit (end of dosing). Until this blood work is accomplished, the effects of 4.5% eyelid testosterone gel applied BID will remain unknown.

Research Rationale

Androgen, especially when topically applied to the eyelids, appears to be effective in management of dry eye disease due to its impact on function of tear apparatus.⁷ The results of systemic dermatological application of androgen in the treatment of DED are mixed due to the varying testosterone concentrations and dosage time frames. These studies⁹⁻¹¹ of non-ocular dermatological application of androgen have shown desirable effects and a good safety profile.

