The test formulation will be marketed Natesto gel, containing 5.5 mg testosterone per pump (17 β -Hydroxyandrost-4-en-3-one; inactive ingredients are castor oil, oleoyl polyoxylglycerides and colloidal silicone dioxide; Natesto package insert). The placebo is the exact same formulation without 17 β -Hydroxyandrost-4-en-3-one. The drug and placebo will be delivered to and dispensed by Caduceus Medical group in Yorba Linda for MBKU's study use.

Dosage regimen

One dose per eyelid of masked gel, which is one pump from the dispenser, represents 5.5 mg for each eyelid, will be applied on the surface of upper and lower eyelid skin each eye twice per day (separated by 8 hours) for a total daily dose of 22mg.

Duration

2-week screening period; 4-week masked treatment phase, 8-week washout phase.

Overall study duration 14 weeks

Visit schedule (see Table 4 and 5)

- Visit 1: Screening visit (Day -14)
- Visit 2: Baseline (Day 0) : the drug (placebo) is prescribed and dispensed.
 Instructions are given on how to properly apply the drug. Subjects are instructed to keep the container even if the drug is finished. All containers need to be checked in the following two visits (visit 3 & 4)
- Visit 2a: serum blood draw for baseline total testosterone level, hematocrit, lipid panel, PSA for men only at clinical laboratory

- Visit 3: Two-week visit: check the drug (placebo) to see if supplement needed.
 Empty containers need to be collected.
- Visit 4: Week 4: the drug (placebo) is discontinued. All dispensed containers need to be collected.
- Visit 4a: serum blood draw for treatment period total testosterone level at clinical laboratory (must be in AM, and must be within two hours of application)
- Visit 5: Week 8: 4-weeks washout phase follow up
- Visit 6: Week 12: 8-week washout phase follow up

Evaluation criteria

Efficacy measures

Primary

- Fluorescein tear breakup time (FTBUT)
- MGD secretion grade (0-24 scale)

Secondary:

- 1. Schein Questionnaire and Ocular Surface Disease Index (OSDI)
- Corneal and conjunctival staining as per the Oxford and National Eye Institute (NEI) schemes
- Tear Meniscus Height (TMH) utilizing Keratography 5M (K5M Oculus, Inc Arlington,WA)
- 4. Eyelid signs grading of orifice metaplasia, vascularity, plugged orifice, lid margin irregularity, ridging between orifices, and antero-posterior orifice displacement
- 5. Meiboscore utilizing K5M
- 6. Schirmer I test without anesthetic

Exploratory:

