- Comparison of National eye Institute (NEI) to Ocular Staining Score (OSS) (DEWS II recommendation) staining scheme for efficiency
- 2. Repeatability of the above two staining schemes and meibomian gland secretion scores

Pharmacokinetic measures

• The patients will have blood samples (20 ml) drawn for the determination of total serum testosterone. Blood will be drawn at baseline and within two hours of dose application at Week 4 visit.

Safety measures

- Adverse events (treatment related and treatment unrelated)
- Visual acuity (BCVA ETDRS)
- Biomicroscopy
- Ophthalmoscopy exam
- IOP
- Male scalp hair evaluation
- Female hair evaluation (upper lip, chin, cheeks, scalp)

Subjects

Subjects will consist of a convenience sample of patients over 18 years old with signs and symptoms of dry eye disease (DED). Moderate to severe dry eye subjects who have either aqueous tear deficiency or evaporative dry eye related to meibomian gland

dysfunction will be recruited. The diagnosis of DED is made according to the DEWS II diagnostic criteria based on:

- 1. DE symptomatology: OSDI score \geq 13 and Modified Schein score \geq 7.5
- 2. Plus one of the following:
 - a. NIBUT < 10 seconds or fluorescein breakup time ≤ 6.0 seconds or
 - b. Osmolarity \geq 308 mosm/L in either eye or intraocular difference > 8 mosm/L or
 - Ocular surface staining (SICCA scale) > 5 corneal spots, > 9 conjunctival spots
 - d. Conjunctival-corneal epithelial damage (fluorescein, rose bengal, or lissamine green staining score >3 points).
- 3. Subtype Tests: severity according to the DEWS II Dx report;⁴ page 556
 - a. Aqueous tear deficiency: non-invasive meniscus height (TMH) ≤ 0.2 mm
 - b. Evaporative: only moderate to severe included:
 - Moderate: 1) orifice plugging, 2) lid margin vascularity, 3) gland secretion grade 8 – 12 (central 8 glands, 0 – 3 scale each),
 4) expressibility grade 2
 - Severe: 1) lid margin dropout or displacement, 2) gland secretion score ≥ 13, 3) expressibility grade of 3

The subjects will be recruited from among students, staff, faculty and patients from Ketchum Health, the clinical facility at Marshall B. Ketchum University. Additionally, the study will be advertised on social media to maximize the recruitment pool, such as Facebook, Instagram, and Twitter. Subjects will be sex-, and age-matched as they are enrolled since these parameters affect dry eye parameters such as marginal changes and meibomian gland secretion. ⁴⁴

Sample size estimation

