- 4. The principal investigator is masked from tests and placebo formulation during the follow up dry eye evaluations on subjects.
- 5. All masked information will only be opened at the end of the study or unless an adverse event (AE) requires unmasking to determine whether the AE was due to the treatment medication.

Study Sites

 Southern California College of Optometry at Main Campus ([name]). Main site for dry eye examination

Inclusion & Exclusion Criteria

Inclusion criteria

There are no restrictions for subject inclusion based on ethnicity, race, or occupation. All subjects meet the following criteria:

- 1. Male or female age over 18
- 2. Able and willing to follow study instructions.
- 3. Are able to provide written informed consent
- 4. Written authorization for use or release of health and research study information will be obtained
- Are willing to discontinue use of artificial tears and makeup on the study visit days
- 6. Able and willing to attend the clinical laboratory for morning blood draws to assay serum testosterone in addition PSA levels for men.
- 7. Patient must have a best corrected visual acuity of 20/40 or better in each eye
- 8. Patients must have normal lid position and closure

- Patients' willingness and ability to cooperate with the investigator and follow all instructions
- 10. A negative urine pregnancy test result for women of childbearing potential
- 11. Women of childbearing potential (from 18 to 50 years old) must have a history of bilateral tubal ligation or use contraceptives, implants, injectables, transdermal patch or IUD for birth control during the study. Patients taking oral contraceptives must not miss 2 or more doses in a one-month period. If these methods of birth control do not apply, women of childbearing potential must have a monogamous partner who has had a vasectomy at least 3 months before the screening visit. The date of the vasectomy and physician contact information must be documented in the source documents.
- 12. Subjects must have a meibomian gland secretion score of 8 or greater (0 24 scale).
- 13. Subject s must have at least 50% meibomian glands present in the upper eyelids.

Exclusion criteria

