Appendix III: Dry Eye Classification Criteria and Appendix V: Staging the Severity of MGD-Related Ocular Surface Disease

17. General statistical methods and types of analyses

- Comparisons, ANOVA, meibomian secretion scores, meibomian gland dropouts, OSDI
- The primary visit is week 4 and primary efficacy variables are the FTBUT and quality of meibomian secretions
- A two-sided test with p-value less than or equal to 0.05 will be considered as statistically significant.
- 18. Comparisons between pairs of treatment groups will be done with Cochran-Mantel Haenszel (CMH) tests, stratified by the ocular discomfort strata. Within Strata comparisons will be done with Wilcoxon rank-sum tests for both ordinal and continuous variables. For nominal variables, within strata comparisons will be done with Pearson's chi-square or Fisher's exact tests.
- 19. Exploratory pharmacokinetics data analysis
- Summary statistics of testosterone, dihydrosterosterone, and 3-alphaandrostanediol glucuronide serum concentrations will be calculated. The relationships between treatment time and gender will be examined.

Confidentiality

The identity of the subjects will be treated as confidential. The results of the study, including any other data, may be published for scientific purposes but will not reveal the name of the subject or include any identifiable references to the subject. Although

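### The single on-treatment testosterone draw has a two-hour upper limit but no minimum or target time, so compliant Week 4 readings are not assured to be comparable

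*Combined protocol and SAP*

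**What the plan says.** The timing rule appears in three places, each time as an upper limit only.

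- Visit 4a in the Visit schedule: "serum blood draw for treatment period total testosterone level at clinical laboratory (must be in AM, and must be within two hours of application".
- Pharmacokinetic measures: "Blood will be drawn at baseline and within two hours of dose application at Week 4 visit".
- Background, just before Research Rationale: "within two hours of the morning eyelid dose at the four-week visit (end of dosing".

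Table 5 shows blood draws only at baseline and Week 4, so this is the only sample taken on treatment. Under Dosage regimen the gel goes on "twice per day (separated by 8 hours) for a total daily dose of 22mg". Inclusion criterion 6 requires subjects to be "Able and willing to attend the clinical laboratory for morning blood draws to assay serum testosterone", so the draw takes place away from the eye examination.

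The Background gives the draw some weight: "Until this blood work is accomplished, the effects of 4.5% eyelid testosterone gel applied BID will remain unknown". The planned analysis, under Exploratory pharmacokinetics data analysis, is descriptive: "Summary statistics of testosterone, dihydrosterosterone, and 3-alphaandrostanediol glucuronide serum concentrations will be calculated". It makes no adjustment for time since the last application. The available text, including the legible parts of the Appendix III case report form, does not ask for the time of application or the time of draw.

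**The concern.** A draw five minutes after the morning application and one at two hours both comply, and both enter the summary as the same Week 4 value. The first mostly reflects what is left from the previous afternoon; the second reflects substantial fresh absorption. Part of the spread in the summary could then come from clock time rather than from how much testosterone crosses the eyelid skin. If the times are not recorded, this cannot be corrected afterwards.

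What is at stake is the quality of the trial's only exposure reading. It matters mainly in women. The Background quotes a simulated rise of 0.15 to 0.18 ng/ml (for once-daily use) and a normal female range of 0.12 to 0.58 ng/ml, so the rise is 0.15/0.12 = 125% to 0.18/0.12 = 150% of the female lower limit. In men it is at most 0.18/2.54 = 7% of the lower limit.

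**Working it through.** **Inputs from the document.** 5.5 mg per eye per application, two applications a day 8 hours apart, and a draw at any time up to 2 hours after the morning one. The stated daily dose reproduces: 5.5 × 2 eyes × 2 applications = 22 mg. The plan gives no figure for the effect of draw time, so there is none to reproduce.

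**Gap before the morning application.** 24 − 8 = 16 hours, the longest gel-free interval of the day.

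**Assumed inputs.** The documents give no absorption rate, elimination rate or lag for eyelid gel; Appendix I is a separate file. I assumed one compartment, first-order absorption and elimination, linear kinetics and steady state. One application contributes, up to a constant that cancels,

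g(t) = ka/(ka − ke) × (e^(−ke·t) − e^(−ka·t)), with k = ln 2 / half-life (the usual limit when ka = ke).

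The level t hours after the morning application, before the second one, is g(t) + g(t+16) + g(t+24) + g(t+40) + …

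**One case by hand.** Absorption half-life 1 h, elimination half-life 3 h: ka = 0.693, ke = 0.231, ka/(ka − ke) = 1.5.

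- 0 min: g(16) + g(24) + … = 0.037 + 0.006 = 0.043
- 15 min: 1.5 × (0.944 − 0.841) + 0.043 × 0.944 = 0.195
- 60 min: 1.5 × (0.794 − 0.500) + 0.043 × 0.794 = 0.475
- 120 min: 1.5 × (0.630 − 0.250) + 0.043 × 0.630 = 0.597
- Daily peak, at 10.06 h (after the second application): 0.722

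As shares of the peak these are 6%, 27%, 66% and 83%. Two people with identical absorption, drawn at 15 and 120 minutes, differ by 0.597/0.195 = 3.1 fold.

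**Range.** Absorption half-lives of 0.5, 1, 2, 4, 6 and 8 h were crossed with elimination half-lives of 0.5, 1 and 2 h, giving 18 combinations with no lag. The day's lowest level falls at the moment of the morning application in all 18.

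| Minutes after application | Share of daily peak | Ratio to daily average |
|---|---|---|
| 0 | 0-45% | 0-0.59 |
| 15 | 22-67% | 0.42-4.08 |
| 60 | 52-99% | 0.81-5.77 |
| 120 | 47-92% | 0.97-3.12 |

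The next table gives the CV of the gel-derived rise due to draw time alone (SD divided by mean of the level, with times uniform over the window).

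| Window, min | CV range | Median of grid |
|---|---|---|
| 0-120 | 14-40% | 29% |
| 15-120 | 11-28% | 16% |
| 30-120 | 7-22% | 10% |
| 60-120 | 2-20% | 5% |

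Within one person, the highest and lowest readings differ 1.5 to 3.5 fold across 15-120 minutes, and 1.06 to 2.0 fold across 60-120 minutes.

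**Slower kinetics.** With absorption half-lives of 0.25 to 4 h and elimination half-lives of 1.5 to 24 h (25 combinations), the median CV falls from 20% over 0-120 minutes to 3.5% over 60-120 minutes, and it falls in every combination. At the slow end (4 h and 24 h) the level is already 85% of peak at 0 minutes and 90% at 120 minutes, so readings from 15 to 120 minutes differ by only about 5%. Adding a 0.5 h lag moves the lowest level to 0.5 h, still inside the permitted window.

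**The case against.** Much of the case on the other side stands.

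- **No documented kinetics.** A reader might infer that compliant readings cannot be compared at all. The documents do not support that: with a slow depot, timing hardly matters. The grid counts and medians are not probabilities either, since another grid would give others. Only the ranges and the direction carry weight.
- **Very early draws are unlikely.** The draw is at a clinical laboratory, so few may fall in the first 15 minutes. The fair comparison is then 11-28% against 2-20%, not 14-40%. If nearly all draws came after 30 minutes the gain would be smaller still (7-22% against 2-20%).
- **The two-hour limit may come from Appendix I**, which is not available here. Even so, an upper limit alone does not fix a sampling time.
- **A 60-120 minute window is a choice and a partial remedy.** It still allows up to a two-fold difference in one person. It also misses the modelled daily peak, which falls at 8.7 to 11.5 h, after the second application.
- **No decision rests on the result.** The gel stops at Visit 4, no threshold or stopping rule uses the reading, and it is listed under pharmacokinetic rather than safety measures. A 16% CV on a rise of 0.15-0.18 ng/ml is 0.024-0.029 ng/ml, against a female range 0.58 − 0.12 = 0.46 ng/ml wide. Twice-daily use could raise that figure, and between-subject variation is not documented for comparison.

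These points limit the size and importance of the concern. They do not supply a minimum time or a recorded one.

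**Conclusion.** The concern holds as a minor, cheap improvement. The rule has an upper limit only, the dose-to-draw interval is not required to be recorded, and the morning application follows a 16-hour gap. Compliant readings are therefore not assured to be comparable, and a very early one can sit near the day's lowest gel-derived level. Under the assumed half-lives, timing alone contributes a CV of about 11-28% over 15-120 minutes, or 14-40% if draws in the first 15 minutes occur. Over 60-120 minutes it is 2-20%. With a slow skin depot the difference is slight.

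A reader might also infer that the trial will understate exposure, or will wrongly place women inside their normal range. Neither follows. Early draws fall below the daily average at 0 minutes in every case modelled, but later ones in the same window can exceed it. Any misclassification rate would depend on baseline levels, and on whether the simulated 0.15-0.18 ng/ml is a peak or an average, which the text does not say. The effect is confined to the exploratory exposure summary, mainly in women. The efficacy analyses are untouched.

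**What to change.** In the Background, the Visit schedule (Visit 4a) and Pharmacokinetic measures, replace the open two-hour limit with a window that has a lower bound. An example is 60 to 120 minutes after the morning application, or a window around the time to peak in the Appendix I simulation if that points elsewhere. Saying explicitly that the draw comes after the application also rules out a pre-dose sample.

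Record the clock times of application and draw with the laboratory result, and summarise samples outside the window separately. Report the value as a level at that time after the morning application, not as a daily peak or average. Leave the timing of the gel relative to the Week 4 eye examination as it is.

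The cost is a change of wording in three places, two recorded times and slightly tighter scheduling of the laboratory visit. No extra visit or blood sample is needed.

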- In this present investigation the principal outcome measures, fluorescein TBUT (using 2.0 microliters of 1.0% sodium fluorescein) and the system for meibomian gland secretion (0-24 scale) are recommended by the MGD workshop and DEWS II diagnostic committees.⁴ Table 2 shows the sample size estimation with two arm parallel design, comparing the change from baseline in FTBUT in each arm with a two sample t-test continuous data, clinically meaningful change of 2.5 seconds with Standard Deviation (SD) following treatment of 2.5 seconds. The results are as follow:
- 2-Sample t Test
- Testing mean $1 = \text{mean } 2 \text{ (versus } \neq \text{)}$
- Calculating power for mean 1 = mean 2 + difference
- $\alpha = 0.05$
- Assumed standard deviation = 2.5

Table 2: Sample size estimation

_	Difference	Sample Size	Target Power	Actual Power
	2.0	26	0.8	0.807487
	2.5	17	0.8	0.807037
	3.0	12	0.8	0.802079
	3.5	10	0.8	0.841306

4.0

0.8

0.844793

- 2.
- 3. With the actual power of 0.807, total of 34 subjects with seventeen (17) subjects per arm will be recruited for this study.

8

Randomization method

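### The stated power of 0.807 is for a two-sample t-test of FTBUT change, but the analysis section names no t-test and describes stratified CMH and Wilcoxon tests

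*Combined protocol and SAP*

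**What the plan says.** Under Sample size estimation, the trial is sized by "comparing the change from baseline in FTBUT in each arm with a two sample t-test continuous data", using a "clinically meaningful change of 2.5 seconds with Standard Deviation (SD) following treatment of 2.5 seconds". Table 2 gives 17 per arm for that difference, and the section concludes "With the actual power of 0.807" that 34 subjects will be recruited.

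Under General statistical methods and types of analyses (items 17 and 18), week 4 is the primary visit and FTBUT and meibomian secretion quality are the primary variables. The significance rule is "A two-sided test with p-value less than or equal to 0.05". Three statements bear on method:

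- A bullet reads "Comparisons, ANOVA, meibomian secretion scores, meibomian gland dropouts, OSDI". FTBUT is not in it.
- Item 18 says "Comparisons between pairs of treatment groups will be done with Cochran-Mantel Haenszel (CMH) tests, stratified by the ocular discomfort strata".
- Item 18 adds that, within strata, "comparisons will be done with Wilcoxon rank-sum tests for both ordinal and continuous variables".

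No t-test is mentioned there. The discomfort strata are neither defined nor counted, and the type of CMH score is not given. The covariates under Randomization method are sex and age, not discomfort.

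**The concern.** FTBUT is a continuous primary variable and the only endpoint on which the trial was sized. Read literally, item 18 sends its between-arm comparison to a stratified CMH test, while the power statement belongs to a t-test. The stated power exceeds the target by only 0.807 − 0.80 = 0.007, so a small loss of efficiency from changing the test is enough to cross 0.80.

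Two things are at stake. First, a reader cannot tell what power the analysis as written has. Second, with a t-test in one section and ANOVA, CMH and Wilcoxon in another, the choice of primary FTBUT test is open until the data from 34 subjects have been seen, and p-values near 0.05 can differ between these tests.

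**Working it through.** **Inputs from the documents.** Difference 2.5 s, SD 2.5 s, 17 per arm, target power 0.8 (Sample size estimation and Table 2); two-sided 0.05 (General statistical methods).

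**Inputs assumed, because the documents do not give them.** Number of strata (2 to 4), CMH score type, how far the strata predict FTBUT change, and the shape of the outcome distribution.

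**Step 1: reproduce the plan's figure.** For a two-sample t-test the noncentrality is (difference / SD) × √(n/2) = (2.5 / 2.5) × √(17/2) = √8.5 = 2.915, on 2 × 17 − 2 = 32 degrees of freedom. Exact noncentral-t power is 0.807037, as in Table 2. The other rows also reproduce: 0.807487 (n = 26), 0.802079 (n = 12), 0.841306 (n = 10), and 0.844793 if the last row, whose n is not legible in the text, is n = 8. Table 2 is correct for a t-test.

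**Step 2: power of the CMH test at 17 per arm.** In each stratum, with N subjects of whom n₁ are on active treatment, let D be the sum of scores on active treatment minus n₁ × the stratum mean score, and V = n₁(N − n₁)/N × the variance of the scores. The test rejects when (ΣD)²/ΣV ≥ 3.841. Ranks within stratum divided by (N + 1) give the van Elteren form; raw values give the mean-score form. Power was simulated at a standardised difference of 2.5 / 2.5 = 1.0, with total SD unchanged, strata of equal expected size and chance allocation to arms within strata. With 12,000 simulated trials the standard error near 0.75 is √(0.75 × 0.25 / 12,000) = 0.004.

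| Setting, 17 per arm | 2 strata | 3 strata | 4 strata |
|---|---|---|---|
| Rank scores, normal data, strata unrelated to outcome | 0.75–0.76 | 0.73 | 0.70–0.71 |
| Raw scores, normal data, strata unrelated to outcome | 0.79 | 0.77 | 0.76 |
| Rank scores, normal data, strata explain 10% of variance | 0.80 | 0.78 | 0.75 |
| Rank scores, normal data, strata explain 20% of variance | 0.84 | 0.82 | 0.79–0.80 |
| Rank scores, heavier tails (t with 5 df, same SD), strata unrelated to outcome | 0.84 | 0.81 | 0.79 |

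If strata unrelated to outcome happen to be balanced between arms, the rank-score figures with normal data rise to 0.77, 0.76 and 0.74, and the raw-score figures to about 0.80 throughout.

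**Step 3: reference points.** An unstratified Wilcoxon test on normal data has power of about 0.78 at 17 per arm, although the plan does not propose one. A two-group ANOVA on change is the same test as the t-test, so its power is 0.807. A Wilcoxon test inside a single stratum of 8 or 9 per arm has about 0.44 to 0.49.

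**The case against.** The strongest objection is that no shortfall follows from the plan. A reader might infer that the trial misses its 0.80 target even if every sizing assumption is met. The documents do not support that. Keeping the difference, SD, alpha and sample size as stated, strata that explain 20% of the variance give about 0.79 to 0.84, and heavier tails give a similar range. The 0.70 needs rank scores, four strata, strata unrelated to outcome and normal data all at once, and the first three appear nowhere in the documents. Baseline discomfort may or may not predict FTBUT change; the plan does not say. This objection stands, and the power figures must be read as conditional.

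A second objection is that the analysis section is too fragmentary to show that FTBUT will be tested by CMH. The ANOVA bullet reads like a loose list, item 18 speaks of pairs of groups in a two-arm trial, and the sample size section itself describes a t-test of FTBUT change. This also stands in part: the fair description is an inconsistency, not a settled choice of a rank test. It does not remove the point, because item 18 is worded to cover continuous variables and the ANOVA bullet leaves FTBUT out.

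A reader might also take the 0.44 to 0.49 as the power of the primary analysis. The plan does not say that the primary conclusion rests on a within-stratum test.

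None of these objections makes 0.807 the power of the analysis as written. If the true power were higher, the statement would still refer to another test.

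**Conclusion.** The point holds as an inconsistency between sizing and analysis. Table 2 is arithmetically correct for a two-sample t-test, but the analysis section describes a stratified CMH test with within-stratum Wilcoxon tests, so the stated 0.807 does not describe it.

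The size of the effect cannot be fixed from the documents. Under Table 2's inputs with normal data, rank scores and strata unrelated to outcome, power is about 0.76, 0.73 and 0.70 for 2, 3 and 4 strata, a loss of roughly 0.05 to 0.11 from 0.807. Raw scores with the same strata give about 0.76 to 0.79. Strata explaining about 20% of the variance restore the rank test to about 0.79 to 0.84. The change therefore runs from a moderate loss to a small gain. This is worth correcting before analysis, but it does not show that the trial is too small.

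**What to change.** State under General statistical methods that the primary FTBUT analysis is the between-arm comparison of change from baseline to week 4 by two-sample t-test or its linear-model equivalent, two-sided at 0.05, with the CMH and Wilcoxon tests as sensitivity analyses. Table 2 and the 0.807 then stand as written. The cost is one sentence and no subjects. The discomfort strata still need a definition for the sensitivity analyses.

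If the stratified rank test is to remain primary, define the strata and the CMH scores, and restate the power under Sample size estimation for that test with its assumptions. The cost is a different power figure, and possibly a few more subjects if 0.80 is to be kept. As an illustration only, with normal data, rank scores and strata unrelated to outcome, 19, 20 and 21 per arm give 0.813, 0.807 and 0.809 with 2, 3 and 4 strata, or 38, 40 and 42 subjects in total against the planned 34.

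### The stated power of 0.807 rests on an SD that is not defined and on no loss of subjects, and the planned analysis is neither the test that was sized nor adjusted for baseline FTBUT

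*Combined protocol and SAP*

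**What the plan says.** Under "Sample size estimation", the trial is sized by "comparing the change from baseline in FTBUT in each arm with a two sample t-test continuous data". The difference is a "clinically meaningful change of 2.5 seconds" and the spread is a "Standard Deviation (SD) following treatment of 2.5 seconds". The software output below it repeats only an assumed SD of 2.5. Table 2 gives 17 per arm and power 0.807037 for this case, and the section concludes that a "total of 34 subjects with seventeen (17) subjects per arm will be recruited for this study". No source for the SD, no baseline SD, no correlation between baseline and week 4, and no allowance for loss appears in the available text.

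The statistical hypotheses are framed as change from baseline to week 4. The section on general statistical methods names week 4 as the primary visit, lists ANOVA without a model, and plans CMH tests stratified by ocular discomfort. It adds: "Within Strata comparisons will be done with Wilcoxon rank-sum tests for both ordinal and continuous variables". It names no t-test and no covariate. The randomization section, by contrast, adopts covariate-adaptive allocation on sex and age group because their influence needs controlling.

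**The concern.** Three things stand between the quoted power and the trial as planned.

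1. **The SD is not identified.** A t-test on change needs the SD of change. The words used could describe that, or the spread of FTBUT values at week 4. The two can differ materially, and the documents contain nothing to convert one into the other.
2. **Recruitment equals the analysis requirement.** The calculation has only 0.007 of power above its 0.80 target, so there is almost no room for a missing week-4 value.
3. **The sized test is not the planned test.** The figure 0.807 belongs to an unadjusted t-test that the analysis section does not name. The planned methods also leave baseline FTBUT, sex and age group out as covariates, although all three are collected and two drive the allocation.

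At stake is whether a trial of 34 people has the power it reports for a primary endpoint, and whether precision available from data in hand goes unused.

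**Working it through.** **Inputs from the plan:** difference 2.5 s; SD 2.5 s; two-sided alpha 0.05; 17 per arm. **Assumed, because the plan does not give it:** the baseline to week-4 correlation r, shown as a range. Equal baseline and week-4 SDs are also assumed unless stated.

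**Step 1. Reproduce the plan's figure.** The noncentrality is 2.5 / (2.5 × √(1/n₁ + 1/n₂)) with n₁ + n₂ − 2 df. At 17 per arm it is 2.915 on 32 df, giving power 0.807037, as in Table 2. The other rows of the table also reproduce. The arithmetic is sound.

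**Step 2. If 2.5 s is the SD of change, vary the evaluable number.**

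| Evaluable | t-test power |
|---|---|
| 17 + 17 | 0.807 |
| 17 + 16 | 0.794 |
| 16 + 16 | 0.781 |
| 15 + 15 | 0.753 |

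One loss is enough to miss 0.80. Fifteen per arm means 4 of 34 lost, or 12%.

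**Step 3. If 2.5 s is the week-4 SD, all 34 evaluable.** With equal SDs, the SD of change is 2.5 × √(2(1 − r)).

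| r | SD of change (s) | t-test power |
|---|---|---|
| 0.3 | 2.96 | 0.666 |
| 0.5 | 2.50 | 0.807 |
| 0.7 | 1.94 | 0.954 |

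Without equal SDs, the SD of change equals the week-4 SD when r = SD_baseline / (2 × SD_week 4). For an assumed baseline SD of 1.5 s the threshold is 1.5 / (2 × 2.5) = 0.30. As a check, √(1.5² + 2.5² − 2 × 0.30 × 1.5 × 2.5) = √6.25 = 2.5 s. A narrower baseline spread therefore lowers the correlation needed.

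**Step 4. ANCOVA of week-4 FTBUT on arm, baseline, sex and age group.** Three further df are spent. The residual SD is 2.5 × √(1 − r²) if 2.5 s is the week-4 SD. If 2.5 s is the SD of change, the common SD is 2.5 / √(2(1 − r)), so the residual SD is 2.5 × √((1 + r)/2). No gain is credited to sex or age.

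| Reading of 2.5 s | r | 17 per arm | 16 per arm | 15 per arm |
|---|---|---|---|---|
| Week-4 SD | 0.3 | 0.840 | 0.815 | 0.788 |
| Week-4 SD | 0.5 | 0.902 | 0.883 | 0.860 |
| Week-4 SD | 0.7 | 0.976 | 0.968 | 0.958 |
| SD of change | 0.3 | 0.937 | 0.922 | 0.904 |
| SD of change | 0.5 | 0.902 | 0.883 | 0.860 |
| SD of change | 0.7 | 0.863 | 0.841 | 0.815 |

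Estimating the baseline slope in so small a sample inflates the variance by about 1 + 1/(2n − 4), which takes up to about 0.02 off these figures.

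**Step 5. Where ANCOVA falls short.** At 15 per arm, power is 0.766 at r = 0.2 on the week-4 reading and 0.792 at r = 0.8 on the change reading, before the slope cost.

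**The case against.** The strongest reply is that the sentence can be read as the SD of the change after treatment. On that reading the calculation is correct, and 0.807 is right with 34 evaluable. This stands. A reader might infer that the plan used the wrong SD, or that true power is 0.67. The documents support neither: 0.67 needs the week-4 reading, equal SDs and r = 0.3 together, and none of these is stated. The entry criteria allow a low FTBUT as one of several qualifying signs, so a narrower baseline spread is plausible though not certain.

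It can also be said that full evaluability is not always needed. On the week-4 reading with r = 0.7, even 14 per arm gives 0.908 by the t-test. That is also true, but it depends on a correlation that the plan does not give.

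Baseline is not wholly ignored either. The hypotheses concern change, so it enters by subtraction. What is missing is adjustment for it as a covariate.

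Finally, a reader might conclude that ANCOVA secures the stated power for nothing. It does not. On the week-4 reading with r near 0 it gives about 0.79 to 0.80 even with all 34, and Step 5 shows shortfalls after losses on both readings.

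**Conclusion.** The point holds as a matter of unstated conditions, not as an arithmetic error. The figure 0.807 is correct for an unadjusted t-test if the SD of change is 2.5 s and nobody is lost. The plan states neither condition, and it plans different tests. With an SD of change of 2.5 s, realistic losses bring the t-test to 0.75 to 0.78 at 15 to 16 per arm. On the other reading, power with no losses runs from 0.67 to 0.95 for r from 0.3 to 0.7 with equal SDs.

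These are powers of the test used for sizing. The power of the stratified CMH and Wilcoxon plan cannot be derived from what is given. ANCOVA exceeds the change-score t-test at every correlation tabulated, on both readings, but it is an efficiency gain and not a guarantee of 0.80. The change is advisable; its absence does not invalidate the trial. The results rest on approximate normality and, in Steps 3 and 4 except where noted, equal SDs at the two visits.

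**What to change.** 1. Name ANCOVA of week-4 FTBUT on arm, baseline FTBUT, sex and age group as the primary FTBUT analysis, and reconcile the general statistical methods section with it, saying what role, if any, the CMH, Wilcoxon and ANOVA methods keep for this endpoint.
2. State whether 2.5 s is the SD of change or of the week-4 value, and give its source.
3. Replace the single figure 0.807 with the power of that ANCOVA at a realistic evaluable number, for example 15 to 16 per arm, over a stated range of correlations. Quoting the unadjusted t-test power would describe an analysis no longer planned.

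**Cost:** revised wording, three further degrees of freedom, and possibly a less favourable stated power. Baseline FTBUT, sex and age are already collected, so no patients, visits or data are added.
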